2 PARTICIPANTS

2.1 Participants. Describe the general characteristics of the subject populations or groups, including age range, gender, health status, and any other relevant characteristics.

60 children, ages 7-11 years, with persistent asthma and one parent will be recruited for this study. Participants will need to live in King, Pierce, or Snohomish County in Washington State.

Every effort will be made to recruit racial and ethnic minorities; asthma affects all races and ethnicities, with boys and non-Hispanic black children experiencing the highest prevalence. To ensure inclusion of racial and ethnic

minority participants, advertising will particularly target diverse population areas as identified by census tract data.

2.2 Inclusion and exclusion criteria.

a. **Inclusion criteria.** Describe the specific criteria that will be used to decide who will be included in the research from among interested or potential subjects. Define any technical terms in lay language.

Parent/Caregiver Inclusion Criteria

Child's primary caregiver residing with the child (50% or more); ≥ 18 years; speaks and reads English; has a smartphone with data plan; and has a parent-reported asthma responsibility mean score ≤ 2.5 (parent assumes the majority of asthma management responsibility). Participants seeking in person visits must reside within King, Pierce, and Snohomish Counties in Washington State, remote visits will be offered outside of those areas.

Child Inclusion Criteria

1) aged 7-11 years, 2) diagnosis of persistent asthma, defined as a prescription for a daily asthma medication; 3) speak English.

b. **Exclusion criteria.** Describe the specific criteria that will be used to decide who will be excluded from the research from subjects who meet the inclusion criteria listed above. Define any technical terms in lay language.

Parent/Caregiver Exclusion Criteria

None.

Child Exclusion Criteria

Parent report of conditions that impair the child's ability to learn shared-management including: 1) developmental delay (e.g., language < 5 -year level), 2) co-morbid condition (cancer, diabetes, autism); or 3) current asthma exacerbation at the time of recruitment (defined as a prescription for oral corticosteroids) as this is a serious health event and not an opportune time for learning shared management.

2.3 Prisoners.

IRB approval is required in order to include prisoners in research, even when prisoners are not an intended target population.

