expected lung functioning, spirometers use a reference database that requires patient details including age, gender, height, weight. The parent will be instructed to input the study # (instead of name), year of birth (not date) to avoid unnecessary PHI disclosure. The study team will coach the child through spirometry and request that the results be sent to the study team (via email or text). Note, study team will make every effort to perform spirometry outside (weather permitting) and remain socially distanced and advised to wear masks for spirometry, since it is considered an aerosolizing procedure.

Next, individual data collection will commence. Parent participants will be provided an iPad with the electronic instruments preloaded and instructed to complete the instruments to the best of their ability. If questions arise, the study team will answer as needed. The study team will then work 1:1 with the child and assist with instrument completion (reading items, if requested). This technique has been used successfully in [name] other prior dyadic study designs to preclude parental interference in child items. Full instrument descriptions and timepoints are outlined in table below. Estimated time burden: Parent: 50-55 minutes; Child: 40-50 (plus 30-40 if cognitives added).

Assignment

REDCap randomization module will be used to assign dyads to groups using an externally generated block randomization scheme (stratified by sex). After surveys are complete, the study team will assign dyads to intervention or control by selecting “randomize” within REDCap and proceeding with the following, depending on assignment:

Control

Dyads assigned to the usual care control group will be advised of their assignment. An information sheet will be provided that outlines the upcoming data collection sessions (T1 at 8 weeks and T2 and 16 weeks) with compensation amounts. They will be advised to keep the spirometer to use in future visits, and more frequently if they choose. The PI will send the parent an asthma control assessment, based upon spirometry and asthma status questions (C-ACT), with interpretation using the national asthma guideline standards. This report may be shared with the child's health care provider, if desired. Finally, the family will be advised that at the end of the 16 week study period, they will be offered access to the IMPACT system, including the app and wearable device, should they wish to use it.

Intervention

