5.4 Data variables. Describe the specific data that will be obtained (including a description of the most sensitive items). Alternatively, a list of the data variables may be uploaded to **Zipline**.

App usage – login date and duration, management goals selected, anticipated barriers, progress reports, asthma check ins, C-ACT scores, spirometer results, reported medication use.

Document Date & Version

04/29/2021

Version 3.3

Researcher Date & Version

08/16/2021

Version 1.2

APPLICATION IRB Protocol

Page 20 of 56

Instrument details

Construct	Instrument	Time	T0	T1	T2
Demographics					
NINR Demographics	Parent (race, ethnicity, marital status, employment); Child (birthdate, education, race, ethnicity, asthma history) (P)	5	X		
Child Weight, Height	Stadiometer (D) to measure child height (for spirometry), Scale (D) to measure child weight	5	X X	X X	X X
Shared Management					
Asthma Responsibility	Asthma Responsibility Questionnaire (ARQ) (P, C): 10-items, 5-point scale to report asthma management task responsibility, higher scores indicate higher asthma management responsibility for child. Established construct validity; IC reliability $\alpha=.78$ (child), $.84$ (parent).	<5	X	X	X
Asthma Management	Brief Illness Perception Questionnaire (BIPQ) (P,C): 8-item scale to assess beliefs about asthma, with higher scores indicating more burdensome perception.	<5	X	X	X
	Beliefs about Medicines Questionnaire (BMQ) (P,C): 10-item, 5-point scale to assess medication beliefs and concerns, with higher scores indicating higher perceived necessity or concerns.	<5	X	X	X
Self-Efficacy	Asthma Management Self-Efficacy (P, C): 13-items (parent) and 12-items (child), 5-point scale assesses asthma self-efficacy, higher scores indicate higher self-efficacy. Construct validity; IC reliability $\alpha=.87$ (child), $.87$ (parent).	<5	X	X	X
Medication Adherence	Medication Adherence Report Scale for Asthma (MARS-A) (P, C): 10-items, 5-point scale assessing reported asthma controller medication adherence. $M \geq 4.5$ indicates adherence; IC reliability $\alpha=.68$ (child); $.74$ (parent).	<5	X	X	X
Family Functioning	Family Assessment Device (P): 60-item validated instrument using 4-point Likert scale, with higher scores indicating worse levels of family functioning.	10-15	X	X	X
Daytime Function & Health Outcomes					

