Asthma control	Childhood Asthma Control Test (C-ACT) (P, C): 7 total items--3 parent (5-point scale) and 4 child (3-point scale)-- assess asthma control, higher scores indicate better control. IC reliability $\alpha=.79$.	<5	X	X	X
	Child spirometry (D) – objective measure of expiratory lung function.² Asthma control (FEV₁:FVC) will follow national spirometry guideline cutpoints.²	5	X	X	X
Asthma-Related Quality of Life	Pediatric Asthma Quality of Life Questionnaire (P, C): 13 items, 7-point scale, parent or child-reported tools measuring quality of life of child/parent of child with asthma. Higher scores indicate higher QOL.	<5	X	X	X
OPTIONAL COGNITIVE BATTERY – in person only					
Executive Functioning	NIH Toolbox Cognition Battery (C): 30 min battery measures attention, processing speed and working memory in game-like format. Validated for ages 3-15 years, administered via iPad.	30-40	X	X	X
IMPACT Usability & Acceptability					
Acceptability	Feasibility and Acceptability of Intervention Measures (FIM, AIM) (P, C): 8 items using 5-point scale; higher scores indicate higher feasibility or acceptability. Established validity, reliability.	<5		I	
Usability	System Usability Scale (P): 10-items, 5-point scale to report usability of system. Higher scores indicates higher usability. Established validity, reliability.	<5		I	
Overall	Semi-structured Interview (P,C): 12 semi-structured questions to be used in post-intervention interview with parent and child.	10-15		I	
(P) Parent report, (C) child report, (D) direct measurement; I= intervention group only; C= control group only					

5.5 Data sources. For all types of data that will be accessed or collected for this research: Identify whether the data are being obtained from the subjects (or subjects' specimens) or whether they are being obtained from some other source (and identify the source).

If you have already provided this information in Question 5.1, you do not need to repeat the information here.

Direct measurement: child weight, height, spirometry, NIH Cognitive battery (optional)

Self-report: all surveys/questionnaires

IMPACT app use – site tracks unique ID logon date, time, duration, use (goals selected, progress, asthma symptom reports, asthma control – C-ACT and spirometry, medication use)

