It is a reasonable expectation that some child subjects may experience an asthma exacerbation (attack) during the study. Study subjects will be told that the intervention does not replace medical advice and that any concerns with their treatment should be discussed with the child's health care provider. For an emergency, call 911. While the IMPACT app tracks asthma data (spirometry and C-ACT data regarding asthma control), a disclaimer is present on the app that advises the app does not replace sound clinical judgement and provider recommended care. Should a family contact the 24- hour study team phone number, they will be advised to contact their provider and/or seek immediate care.

Mild discomfort related to symptom watch (intervention child subjects only):

The watchband may irritate the skin and participants will have the option to wear it over a long sleeve shirt. Skin reactions of this kind are unusual, and [name] will be available to troubleshoot with participants as needed. Alternative watch bands may also be provided.

Anxiety or fatigue while completing surveys:

Questionnaires are routinely used in research, and pose no risks, though certain questions in the questionnaires explore health history of medical and/or psychological illness, family functioning. Participants may choose not to answer any questions causing discomfort, and may stop questionnaires at any time. If fatigued, subjects will be offered breaks. Additionally, subjects will be advised that there are no "correct" or "right" answers.

Stress about completing spirometry (child participants):

Spirometry is a routine measure of lung function used in both clinical practice and research, and poses no risks. However, children may feel fatigued or stressed when performing the maximal exhalations. The spirometer has visual incentives (such as blowing out candles or inflating a balloon) to assist with completion. However, the child participants may choose to discontinue at any time.

Social Risks

To minimize embarrassment or anxiety about the symptom watch, child intervention participants may wear a long sleeve shirt over the watch.

10.2 Reproductive risks.

Are there any risks of the study procedures to men and women (who are subjects, or partner of subjects) related to pregnancy, fertility, lactation or effects on a fetus or neonate?

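### The visible protocol and SAP list no measure of asthma exacerbations after baseline in either arm and no summary of them by arm, although the protocol expects them to occur

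*Protocol*

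**What the plan says.** - **The event is expected.** Protocol section 10.1, on asthma exacerbation: "It is a reasonable expectation that some child subjects may experience an asthma exacerbation (attack) during the study".
- **It is defined and treated as serious.** The child exclusion criteria in section 2.2b refer to "current asthma exacerbation at the time of recruitment (defined as a prescription for oral corticosteroids) as this is a serious health event". Section 4.6 repeats the criterion as a screening item. The definition is not used again after enrolment.
- **The instrument table is presented as complete.** Section 5.1 states "Full instrument descriptions and timepoints are outlined in table below". The nearest history item in the section 5.4 table is "Child (birthdate, education, race, ethnicity, asthma history) (P)", ticked at T0 only.
- **Two asthma status measures are taken in both arms at T0, T1 and T2.** The C-ACT is there to "assess asthma control, higher scores indicate better control", and spirometry is described as an "objective measure of expiratory lung function".
- **The phone line is described by the advice it gives.** Section 10.1: "Should a family contact the 24- hour study team phone number, they will be advised to contact their provider and/or seek immediate care". No step for recording the call is stated.
- **The SAP** analyses responsibility, self-efficacy, adherence, control and quality of life. It names no exacerbation or adverse-event summary.
- **Two relevant items sit elsewhere.** Section 10.6 marks the data and safety monitoring plan (DSMP) as uploaded, and section 5.14 says PDF versions of the REDCap surveys will be attached. Neither is among the documents reviewed.

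**The concern.** Eligible families are those in which the parent carries most of the asthma responsibility (section 2.2a). A higher responsibility score means more of it lies with the child (section 5.4), and the SAP expects scores to rise in the intervention group. Success on a primary outcome is therefore a shift of asthma tasks towards a child aged 7 to 11. Exacerbation is the natural safety counterpart to that shift, and the protocol itself expects some.

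If events are not asked about systematically, the pilot cannot give the next trial an event frequency by arm, and it cannot tell whether a poor C-ACT or spirometry result at T1 or T2 followed a recent attack.

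Falling back on incidental reports would not be even-handed. For 16 weeks only the intervention arm has the app and symptom watch, and only that arm has the T1 interview. An attack in that arm is more likely to come to the team's notice, which could look like harm.

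**Working it through.** The documents give no exacerbation rate, no power calculation and no target precision, so there is no plan figure to reproduce. The check has two parts.

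**1. Is there any listed route by which an exacerbation after T0 is recorded?**

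| Source (protocol unless stated) | Arms | What it gives after T0 |
|---|---|---|
| Questionnaires on responsibility, illness and medicine beliefs, self-efficacy, adherence, family functioning and quality of life (5.4) | Both | Scale scores; no event item described |
| C-ACT and spirometry (5.4) | Both | Control and lung function; no event count |
| Asthma history (5.4) | Both | Nothing; T0 only |
| App and watch data (5.1, 5.4) | Intervention; controls are offered access only at the end of 16 weeks | Symptoms, check-ins, reported medication use |
| Semi-structured interview and usability measures (5.4) | Intervention, T1 | No event item described |
| Medical records (5.7) | Recruitment only | Names, age, email and address |
| 24-hour phone line (10.1) | Both | Advice; no recording step stated |
| SAP | Both | No exacerbation or adverse-event summary |

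Listed instruments that count exacerbations after T0: 0 in each arm.

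**2. What would recording them yield?**

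Inputs: 60 dyads (section 1.5); 16 weeks (section 5.1); retention benchmark of 80% (SAP). Assumed, because the documents are silent: 1:1 allocation, so 30 per arm, or 24 per arm at 80% retention; two-sided alpha of 0.05; 16-week control risk of 5% to 30%; or an event rate of 0.3 to 1.0 per child-year.

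*Expected events.* Exposure is 60 × 16/52 = 18.46 child-years. Events: 18.46 × 0.3 = 5.5 to 18.46 × 1.0 = 18.5, with full retention.

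*Precision.* The 95% half-width for a risk difference at equal risk p is 1.96 × √(2p(1 − p)/n). For p = 0.10 and n = 30: 1.96 × √(0.18/30) = 0.152.

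*Power.* Φ[(d − 1.96 × SE0)/SE1], where d is the absolute risk difference, SE0 uses the pooled risk and SE1 the separate risks. For 10% versus 20% with n = 30:
- SE0 = √(0.15 × 0.85 × 2/30) = 0.0922
- SE1 = √(0.09/30 + 0.16/30) = 0.0913
- (0.10 − 1.96 × 0.0922)/0.0913 = −0.88, so power is 19%

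| Control risk | Half-width, 30 per arm | Half-width, 24 per arm | Power for doubling, 30 per arm (Fisher exact) | Power for halving, 30 per arm | n per arm, 80% power for doubling |
|---|---|---|---|---|---|
| 5% | 11.0 points | 12.3 points | 11% (2%) | 7% | 435 |
| 10% | 15.2 points | 17.0 points | 19% (10%) | 11% | 199 |
| 20% | 20.2 points | 22.6 points | 39% (30%) | 19% | 82 |
| 30% | 23.2 points | 25.9 points | 65% (56%) | 28% | 42 |

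With 30 per arm, 80% power would need a rise from 10% to about 41%, or from 20% to about 54%.

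**The case against.** The strongest reply is that the gap may already be closed in material not available here. A DSMP can require an event question at each visit without that question appearing in the section 5.4 table. Section 10.1 also says some questionnaire items explore medical history, so item content goes beyond the one-line descriptions. This stands, and it limits the point to what the visible protocol and SAP list. A reader might infer that exacerbations will go unrecorded or that the trial will be able to say nothing about them. The documents do not support that.

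A second reply is that this is a feasibility and acceptability pilot of 60 dyads. A reader might infer that the missing item is the reason the trial cannot show whether shifting tasks to the child raised or lowered exacerbations. The power figures above rule that out: complete recording would not settle the direction unless the effect were very large.

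A reader might also infer that the team hears of an attack only if a family rings. It does not follow. The team meets both arms at T1 and T2, asks about concerns before each contact (section 8.2f) and sends both arms an asthma control report with an offer to discuss it (section 10.10). These contacts are unstructured, so they do not produce a count.

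Finally, C-ACT and spirometry give symmetric, indirect information on worsening control, and no between-arm event comparison is planned. Both are true. Neither gives the frequency of an event that the protocol calls serious.

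**Conclusion.** The point holds in limited form. The visible protocol and SAP expect exacerbations and define one, but list no measure of them after baseline in either arm and no summary by arm. The conclusion is conditional on the DSMP and the survey forms, which the sponsor can check directly.

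On an assumed 0.3 to 1.0 events per child-year, roughly 5 to 18 events could occur across both arms. What is at stake is a descriptive count by arm, with intervals of about ±11 to ±23 points on the risk difference at 30 per arm (±12 to ±26 at 24 per arm), not evidence of benefit or harm. All rates and risks are assumptions, as is 1:1 allocation. The change is worth making because it is cheap and missed events are hard to reconstruct later.

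**What to change.** First confirm whether the DSMP or the REDCap surveys already ask about exacerbations identically in both arms. If they do, cite that in section 5.4 and add the by-arm summary to the SAP.

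If they do not:
- Add a short parent-report block to the T1 and T2 surveys, identical in both arms, covering the time since the last study visit: oral corticosteroid prescription (the protocol's own section 2.2b definition), urgent or emergency department visit, and hospital admission, each with an approximate date.
- In the SAP, report descriptive counts by arm with confidence intervals for weeks 0–8 and 8–16, and state that no conclusion about direction of effect will be drawn.
- Exclude app and phone-line reports from the between-arm count.

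Cost: 1 to 2 minutes at each of two existing visits and a minor IRB modification. The counts would rest on 8-week parent recall. Parents know their assignment, so an identical question reduces unequal ascertainment but cannot remove it. No treatment or visit changes.

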11 ECONOMIC BURDEN TO PARTICIPANTS

11.1 Financial responsibility for research-related injuries. Answer this question only if the lead researcher is not a UW student, staff member, or faculty member whose primary paid appointment is at the UW.

For each institution involved in conducting the research: Describe who will be financially responsible for research-related injuries experienced by subjects, and any limitations. Describe the process (if any) by which participants may obtain treatment/compensation.

Not applicable

11.2 Costs to subjects. Describe any research-related costs for which subjects and/or their health insurance may be responsible (examples might include: CT scan required for research eligibility screening; co-pays; surgical costs when a subject is randomized to a specific procedure; cost of a device; travel and parking expenses that will not be reimbursed).

None

12 RESOURCES

12.1 Faculty Advisor. (For researchers who are students, residents, fellows, or post-docs.) Provide the following information about the faculty advisor.

- Advisor's name
- Your relationship with your advisor (for example: graduate advisor; course instructor)
- Your plans for communication/consultation with your advisor about progress, problems, and changes.

Not applicable

12.2 UW Principal Investigator Qualifications. Upload a current or recent Curriculum Vitae (CV), Biosketch (as provided to federal funding agencies), or similar document to the Local Site Documents page in Zipline. The purpose of this is to address the PI's qualifications to conduct the proposed research (education, experience, training, certifications, etc.).

For help with creating a CV, see http://adai.uw.edu/grants/nsf_biosketch_template.pdf and <https://education.uwmedicine.org/student-affairs/career-advising/year-4/residency-applications/curriculum-vitae/>

The CV will be uploaded.

12.3 UW Study team qualifications. Describe the qualifications and/or training for each UW study team member to fulfill their role on the study and perform study procedures. (You may be asked about non-UW study team members during the review; they should not be described here.) You may list these individuals by name, however if you list an individual by name, you will need to modify this application if that individual is replaced. Alternatively, you can describe study roles and the qualifications and training the PI or study leadership will require for any individual who might fill that role. The IRB will use this information to assess whether risks to

subjects are minimized because study activities are being conducted by properly qualified and trained individuals.

Describe: The role (or name of person), the study activities they will perform, and the qualifications or training that are relevant to performing those study activities.

Examples:

Research Study Coordinator: Obtain consent, administer surveys, blood draw. Will have previous experience coordinating clinical research and be a certified phlebotomist in WA.

Undergraduate Research Assistant: Obtain consent, perform all study procedures. Will have had coursework in research methods, complete an orientation to human subjects protections given by the department, and will receive training from the PI or the graduate student project lead on obtaining consent and debriefing subjects.

Acupuncturist: Perform acupuncture procedures and administer surveys. Must be licensed with WA State DoH and complete training in administering research surveys given by the project director, an experienced survey researcher.

Co-Investigator: Supervise MRI and CT scan procedures and data interpretation, obtain consent. MD, specialty in interventional radiology and body imaging. 5-years clinical research experience.

PI will oversee all study procedures, data collection and monitoring. The PI will be responsible for training any study team members on protocols. PI may obtain consent, administer surveys.

Student Assistant – will receive CITI training and mandatory UW background checks, youth training. Will receive training from PI on all study procedures, including strategies for working with parent-child dyads. Obtain consent, perform study procedures, recruit, schedule study sessions, troubleshoot as necessary.

Co-Investigator – review study procedures, enrollment tracking, deidentified data access, interpretation, analyses and dissemination.

12.4 Study team training and communication. Describe how it will be ensured that each study team member is adequately trained and informed about the research procedures and requirements (including any changes) as well as their research-related duties and functions.

There is no study team.

Procedure manuals will be used and checklists for data collection sessions. Any student assistants will be trained by the PI and monitored for adherence to procedures.

13 OTHER APPROVALS, PERMISSIONS, and REGULATORY ISSUES

13.1 Approvals and permissions. Identify any other approvals or permissions that will be obtained. For example: from a school, external site/organization, funding agency, employee union, UW Medicine clinical unit.

Do not attach the approvals and permissions unless requested by the IRB.

NIH/NCATS will review & approve the proposed IMPACT RCT protocol

13.2 Financial Conflict of Interest. Does any UW member of the team have ownership or other Significant Financial Interest (SFI) with this research as defined by [UW policy GIM 10](#)?

No

Yes

→ If yes, has the Office of Research made a determination regarding this SFI as it pertains to the proposed research?

No

→ If no, contact the Office of Research [contact], [contact]) for guidance on how to obtain the determination

Yes

→ If yes, upload the Conflict Management Plan for every UW team member who has a FCOI with respect to the research, to **Zipline**. If it is not yet available, use the text box to describe whether the Significant Financial Interest has been disclosed already to the UW Office of Research and include the FIDS Disclosure ID if available.
